4.13 Exploratory Endpoint Analysis

Continuous exploratory endpoints will be analyzed using the same model as the primary endpoint for the ITT Analysis Set using observed data only. Time from baseline to a decrease in average weekly (NRS) pain of 30% will be compared between treatments using a log-rank test stratified by study center and summarized using Kaplan-Meier estimates. Correlations between pain severity and imaging biomarkers and pain severity and efficacy endpoints will be presented graphically.

4.14 Additional Questionnaire Analyses

The BCTQ and the Survey for Autonomic Symptoms results will be summarized for the ITT Analysis Set using observed data only. Change from baseline in the average Symptom Severity subscale scores and average Functional status subscale scores for the BCTQ will be summarized by treatment and visit. Frequency and percentage of participants reporting at least 1, 2, or 3 symptoms according to the Survey for Autonomic Symptoms will be summarized by gender, treatment, and visit. The change from baseline in total symptom impact score according to the Survey for Autonomic Symptoms will be summarized by gender, treatment, and visit. No formal testing will be performed on the BCTQ or the Survey for Autonomic Symptoms results.

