3.3.2.1.1 Healthy Volunteer (HV) cohorts

In the HV Cohort (Cohorts 1–3 and 8), 53.6% reported at least 1 TEAE, only 1 of which (mild anxiety after 3.0 mg/kg LEVI-04) was considered by Investigator to be related to treatment. There was no evidence of a dose-related effect of LEVI-04 on the incidence of TEAEs in HV.

- The two must frequently reported System Organ Classes (SOCs) of the TEAEs were 'Infections and infestations', and 'Nervous system disorders' with 8 reported TEAEs in each class (7 and 6 participants, respectively).
- The most frequently reported TEAEs in HV cohorts were Headache, reported in 2 participants after Placebo, n=3 after 0.01 mg/kg LEVI-04, and n=1 after 3.0 mg/kg LEVI-04)
- All other TEAEs were reported by only one or two participants each, with no correlation to dose.
- Symptoms of autonomic dysfunction assessed by the Survey of Autonomic Symptoms (SAS) questionnaire occurred in 25.0% of HV on at least one occasion before or after dosing. There was no evidence of a dose-related effect of LEVI-04. One participant before 0.003 mg/kg LEVI-04, One participant before 3.0 mg/kg LEVI-04, Two participants before and after 0.01 mg/kg LEVI-04, Two participants before and after 0.03 mg/kg LEVI-04, One participant after Placebo.

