To evaluate the overall safety of LEVI-04 compared to placebo	AEs between treatment arms (Count and Severity)					

Version

Version 3.0_07FEB2023

Objective(s)	Endpoint(s)
To evaluate the safety of LEVI-04 compared to placebo in relation to the peripheral nervous system	Peripheral Nervous System AEs between treatment arms (Count and Severity)
To evaluate the safety of LEVI-04 compared to placebo in relation to joint safety.	Incidences of Joint Events and subtypes of Joint Events. Events include: Osteonecrosis Destructive Arthropathy, including RPOA type 2 Changes in signs of inflammation on Magnetic resonance imaging (MRI) of the Target Knee, Subchondral insufficiency fracture Rapid loss of JSW by 2 mm within 12 months or loss of 50% of JSW if less than 2 mm at baseline. This is also called RPOA type 1 Any other incidence of joint events such as acute fracture, bone marrow infiltration, etc.

[figure not shown]
5 Investigational Plan

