9.1.9 Adverse Events of Special Interest (AESI)

Owing to the action of LEVI-04 on NGF, neurological AEs are of special interest. The following are considered AESIs:

- AE suggestive of new or worsening peripheral neuropathy
- AE of abnormal peripheral sensation (e.g. allodynia, burning sensation, carpal tunnel syndrome, dysesthesia, hyperesthesia, hyperpathia, hypoesthesia, neuralgia, neuritis, neuropathy peripheral, pall anesthesia, paresthesia, peripheral sensory neuropathy, sciatica, sensory disturbance, sensory loss, or tarsal tunnel syndrome) that is reported as an:
 - o SAE
 - o AE that resulted in the participant being withdrawn from the study.
 - o AE ongoing at the end of study participation in the study or,
 - o AE of severe intensity.
- Destructive Arthropathy, including RPOA type 2
- SIF
- Rapid loss of joint space width (JSW) of 2 mm within 12 months or less, or loss of 50% of JSW if less than 2 mm at baseline. This is also known as RPOA type 1
- Osteonecrosis
- Any incident acute fracture or bone marrow infiltration.
- Total and partial joint replacement

Suspected events will be monitored by the Safety Monitoring Committee, and any events involving joint safety will be escalated to the Independent Adjudication Committee for Adverse Events relating to Joint Safety, for committee review and appropriate recommendations for the individual participant, and potentially the study. The Adjudication Committee for Adverse Events relating to Joint Safety includes at least one rheumatologist and at least one radiologist who are experts in this field as well as the coordinating Investigator and study Medical Monitor or delegates as further described in the Adjudication Committee for Adverse Events relating to Joint Safety Charter.

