10.4.7 Analysis of Safety and Other Endpoints

Safety data will be summarized descriptively overall and by treatment group, using the Safety Analysis Set. No statistical inference will be applied to safety endpoints.

The incidence rate, severity, and relationship to treatment for all AEs will be summarized by MedDRA SOC, and PT. Descriptive statistics will be presented for clinical laboratory tests, vital signs, and physical examinations. The number and percentage of participants with abnormal or potentially clinically significant clinical laboratory values and vital sign measurements will be summarized by treatment. These thresholds will be pre-defined in the SAP.

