4.5 Analysis Sets

The Intention-to-Treat Analysis Set

The Intent-to-Treat (ITT) Analysis Set will include all participants randomly allocated to a treatment, based on the intention to treat "as randomized" principle (i.e., the planned treatment regimen rather than the actual treatment given in case of any difference).

Modified Intention-to-Treat Analysis Set

The Modified Intention-to-Treat (mITT) Analysis Set will include all participants from the ITT Analysis Set who have a baseline and at least one post-treatment WOMAC pain subscale score assessment available.

Per-Protocol Analysis Set

The Per-Protocol (PP) Analysis Set will include all participants from the mITT Analysis Set who have been treated according to the trial protocol and fulfill the following criteria:

- Absence of major clinical trial protocol deviations with respect to factors likely to affect the efficacy of the treatment.
- Adequate compliance with trial medication: participants must have at least four study drug administrations, including an administration at Week 16.

Protocol deviations will be reviewed prior to unblinding to determine which, if any, participants are to be excluded from the Per-Protocol Analysis Set.

Safety Analysis Set

The Safety Analysis Set will include all participants who have been administered at least one dose of trial treatment. Participants will be analyzed according to the actual treatment they receive.

LEVI-04-21-02 Statistical Analysis Plan	Version: Final 3.0
Date: 18-Mar-2024	Page 17 of 34

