4.16 Safety Analyses

Safety will be assessed by adverse events, laboratory assessments (including pharmacokinetic data), vital sign measurements, ECG data, index knee examination, X-Ray and MRI (including but not limited to Minimum Joint Space Width (mJSW) and Incidence of Rapidly Progressive Osteoarthritis (RPOA) Types I and II), and physical examination abnormalities using the Safety

LEVI-04-21-02 Statistical Analysis Plan	Version: Final 3.0
Date: 18-Mar-2024	Page 26 of 34

Analysis Set.

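### The carpal tunnel and autonomic-symptom questionnaires, whose apparent purpose is nerve safety, are summarised by randomised arm while the other safety tables go by treatment received, and the SAP does not say why

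*SAP*

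**What the plan says.** SAP section 4.14 fixes the population for the Boston Carpal Tunnel Questionnaire (BCTQ) and the autonomic survey: "The BCTQ and the Survey for Autonomic Symptoms results will be summarized for the ITT Analysis Set using observed data only". It then asks for descriptive summaries by treatment and visit and rules out formal testing.

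SAP section 4.5 defines the ITT set by "the planned treatment regimen rather than the actual treatment given in case of any difference". For the Safety Analysis Set, which needs one or more doses, the same section says: "Participants will be analyzed according to the actual treatment they receive".

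Protocol section 10.4.7 says: "Safety data will be summarized descriptively overall and by treatment group, using the Safety Analysis Set". SAP section 4.16 applies that set and opens its list of measures with "Safety will be assessed by adverse events, laboratory assessments (including pharmacokinetic data), vital sign measurements, ECG data, index knee examination", going on to imaging and physical examination abnormalities. The two questionnaires are not in that list. SAP section 6, which records changes from the protocol, does not mention their analysis set.

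**The concern.** The two instruments look like safety measures that have been placed on an efficacy population. One safety objective in protocol section 4.1 is "To evaluate the safety of LEVI-04 compared to placebo in relation to the peripheral nervous system". Protocol section 9.1.9 explains: "Owing to the action of LEVI-04 on NGF, neurological AEs are of special interest", and it names carpal tunnel syndrome among the examples. A reader would expect to set the questionnaire tables beside the neurological AE tables, since both bear on the same question.

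As written, the two sets of tables use different grouping rules. A participant randomised to placebo who was given LEVI-04, or one given a different dose level, would be counted under the randomised arm in the questionnaires and under the received treatment in the AE tables. Exposed participants counted as placebo would pull the two questionnaire columns together. Anyone randomised but never dosed could also be counted at baseline in the questionnaire tables and not in the AE denominators.

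**Working it through.** The plan states no figure on this point, so there is none to reproduce. The check is a comparison of text, followed by an illustration of size.

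**Step 1: which rule applies to which data**

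| Data | Set | Grouping | Source |
|---|---|---|---|
| AEs (including AESIs), laboratory, vital signs, ECG, imaging | Safety | Received | SAP 4.16, 4.5; protocol 10.4.7 |
| BCTQ, autonomic survey | ITT | Randomised | SAP 4.14, 4.5 |

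The difference is explicit, and SAP section 6 does not explain it.

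**Step 2: are the questionnaires safety data?** Neither document says so for this trial, so this step is an inference. The evidence for it is:

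- No primary, secondary or exploratory endpoint in protocol section 4.1 or SAP section 2 is mapped to either questionnaire.
- The protocol's Phase 1 account, under its safety and tolerability heading, reports: "Symptoms of autonomic dysfunction assessed by the Survey of Autonomic Symptoms (SAS) questionnaire occurred in 25.0% of HV".
- Protocol section 9.1.9 lists carpal tunnel syndrome under the AESIs.
- In the schedule of events (protocol section 2.1), WOMAC, the staircase test and the global assessment fall at Visits 3, 6 and 10. The two questionnaires fall at Visits 1, 7 and 11.
- SAP section 4.14 plans no formal testing, in line with protocol section 10.4.7, which applies no inference to safety endpoints.

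**Step 3: size if someone is misallocated**

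Inputs: 416 participants randomised 1:1:1:1 (SAP section 4.2) give 416 / 4 = 104 per arm; 624 / 4 = 156 if the sample size is increased. The number misallocated, k, is an assumption, because the documents give no rate.

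Let d be the true mean difference between two arms of n.

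- *One-way.* If k people in the placebo column actually received the active dose, that column's mean moves by (k/n)d, so the tabulated difference is d(1 − k/n).
- *Swaps.* If k people are exchanged each way, both columns move and the difference is d(1 − 2k/n).

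Share of d retained:

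| k | One-way, n = 104 | Swapped each way, n = 104 | One-way, n = 156 |
|---|---|---|---|
| 0 | 100% | 100% | 100% |
| 1 | 1 − 1/104 = 99.0% | 1 − 2/104 = 98.1% | 1 − 1/156 = 99.4% |
| 2 | 1 − 2/104 = 98.1% | 1 − 4/104 = 96.2% | 1 − 2/156 = 98.7% |
| 5 | 1 − 5/104 = 95.2% | 1 − 10/104 = 90.4% | 1 − 5/156 = 96.8% |

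This takes all n participants as observed and gives each misallocated participant the full effect of what they received.

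**Step 4: size if nobody is misallocated**

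Post-dose summaries of observed data are then the same on both sets, apart from any undosed participant who has data. Both questionnaires are collected at Visit 1, so an undosed participant could enter baseline counts. Protocol section 5.4.1 describes the early-termination visit for people who had received study drug, so an undosed participant would rarely have a later score.

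**The case against.** The strongest reply is that no protocol rule is broken. Protocol section 10.4.7 speaks of safety data and then names AEs, laboratory tests, vital signs and physical examinations. Protocol section 7.9 places both questionnaires among the patient-reported outcomes. The lists of safety assessments in protocol section 5.2, protocol section 9, SAP section 1.2 and SAP section 4.16 all omit them. The endpoint mapped to the peripheral nervous system objective is the count and severity of AEs, not a questionnaire score. This part stands: a reader might infer a plain contradiction of protocol section 10.4.7, but the documents support only an inference from the instruments' purpose.

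The second reply is that the main nerve-safety analysis is already sound. The AESIs are tabulated on the Safety Analysis Set by treatment received, and no test or decision rule depends on the questionnaires. That also stands, and it keeps the point minor.

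The third reply concerns frequency. A reader might take 416 × 5 = 2,080 planned infusions as a sign that misallocation is likely. The documents give no dosing-error rate, and neither says how received treatment is assigned when one of five infusions is wrong, so a single error need not move anyone. Randomisation and first dose fall at the same visit (protocol section 8.3.1), so undosed participants should be few. Denominators will in any case differ from those of the AE tables, because the questionnaires use observed data at particular visits.

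None of this gives a reason to prefer the randomised grouping for these two instruments, and the SAP offers none.

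**Conclusion.** The point holds as a mismatch between the questionnaires' apparent safety purpose and their analysis set, left unexplained in the SAP. It rests on one inference, that they serve nerve and autonomic safety. The evidence for that is good, but neither document states it.

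The consequence depends on a participant actually receiving a treatment other than the one randomised. In that case the linked tables disagree and the questionnaire comparison is slightly diluted: two one-way misplacements in an arm of 104 retain about 98% of a true difference, and five retain about 95%. These counts are assumptions. A reader might infer that a nerve signal will be hidden, but the documents give no evidence that misallocation will occur. Without it, essentially only baseline counts could differ. Severity is minor.

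**What to change.** In SAP section 4.14, replace the ITT Analysis Set with the Safety Analysis Set for both questionnaires, grouped by actual treatment received. They then follow the same rule as the AE tables under SAP section 4.16.

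The cost is one phrase in the SAP and one population setting in the table programs. No efficacy analysis, significance level or sample size is affected. If the ITT set is intended, SAP section 6 should say so and give the reason.

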- 8. Planned major surgery or other major invasive procedures while participating in the study
- 9. Surgery or stent placement for coronary artery disease in the six months prior to screening
- 10. Nondiagnostic arthroscopy performed on the target knee joint within 180 days prior to Screening; or diagnostic arthroscopy performed on the target knee joint within 90 days prior to Screening
- 11. Intraarticular injection therapies to the target knee joint within 12 weeks prior to Screening, or to any non-target major joint within 6 weeks prior to Screening
- 12. Participants likely to be deemed unfit for joint replacement surgery due to concomitant illness, in the investigator opinion
- 13. Opioid use, including Tramadol, of 4 or more instances per week over the month prior to Screening
- 14. Known history of hypersensitivity to monoclonal antibodies
- 15. Presence of any medical condition or unstable health status that, in the judgment of the investigator, might adversely impact the safety of the participant or efficacy results of the trial
- 16. Medical history and/or clinical findings (including ECG) of cardiac disease that in the opinion of the investigator are considered of clinical significance, including but not limited to established ischemic heart disease, peripheral arterial disease and /or cerebrovascular disease (unstable angina, myocardial infarction, cardiovascular thrombotic events, transient

Version

Version 3.0_07FEB2023

ischemic attacks, and stroke are considered clinically significant if time of event occured within six months prior to screening)

- 17. Active malignancy or history of malignancy within the past 5 years, with exception of resected and cured basal cell carcinoma and squamous cell carcinoma of the skin
- 18. Clinically significant abnormal laboratory parameter(s) and/or electrocardiogram (ECG) parameter(s) during Screening, that, in the judgment of the Investigator, would preclude the participant from participation in this study
- 19. Participation in other studies involving investigational drug(s) within 30 days (or 90 days for biologics) prior to screening
- 20. History of Carpal Tunnel Syndrome with signs or symptoms within one year of Screening or a Boston Carpal Tunnel questionnaire (Symptom Severity Scale mean score ≥3)
- 21. Total score on Number of Symptoms (Column Q1a) on the SAS >3
- 22. Pregnant or breast feeding
- 23. Previously received any form of anti-Nerve Growth Factor (NGF)

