7.9.3 Survey for Autonomic Symptoms

The Survey of Autonomic Symptoms consists of two columns with two separate scores: A "Number of symptoms score" and a "Total symptom impact score". The first score refers to the total score from column Q1a where the participant answers Y/N to if he/she has had the specific symptom the last 6 months. Yes counts as 1 point, No as 0 and total score for the Number of symptoms score ranges from 0-11 (males) and 0-12 (females). The "Total symptom impact score" is the total score from the second column, Q1b and is scored on impact of the symptoms the participant answered yes to having, ranging from 1 ("not bothered by this symptom") to 5 ("bothered a lot") (total score range 0-60)¹⁸. Both column Q1a and Q1b are to be completed. The Number of symptoms (Q1a) score will be used to determine eligibility, with exclusion of participants with a score of > 3 (4 or more).

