14.2 Appendix II: Protocol Amendments and List of Changes

Protocol and Amendment Versioning

DOCUMENT HISTORY

Document	Date
Version 3.0	07FEB2023
Version 2.0 (not submitted)	05OCT2022
Version DK1.1	24MAY2022
Original Protocol (v.1.0)	09MAR2022

Version 3.0 (07FEB2023)

Overall rationale for the Amendment: Prior to submission of version 2.0 of the protocol, further central inclarities in the protocol arised and the decision to discard submission of protocol version 2.0 and prepare a version 3.0 was made.

Tabulated List of Changes – Version 3.0 (03FEB2023)

Section # and Name	Description of Change	Brief Rationale
Title Page Document headers Section 2: Synopsis Appendix III: Signature Pages and Responsible Persons for the Trial	Updated protocol date/version. Updated contact information.	To incorporate new protocol date and version number and contact information for CRO.
Section 5.4.1: Inclusion Criteria Section 2: Synopsis	Inclusion criterion #12 to specify the probihited use of SNRIs as drug class.	It was unclear if the reference to the generic name for the SNRI, Duloxetine included óther medications within the same drug class.

Version Version 3.0_07FEB2023

Section 5.4.2: Exclusion Criteria	Exclusion criterion #2 rephrased for clarity	Phrasing ambiguous.
Section 2: Synopsis	Exclusion criterion #3 rephrased for clarity	Clarification and specification of which conditions if present should be excluded and which joints it would apply.
	Exclusion criterion #7 rewritten to exclude participants with prior knee allosplasty	Clarification that prior alloplasty of target knee to be excluded.
	Exclusion criterion #21 rewritten to clarify which of the subscores of the scale the criterion refers to and cut-off increased to include a score of 3.	Based on the screening data emerging and the background literature on the SAS, a cut-off of over 3 is considered appropriate.
	Exclusion criterion #27 rewritten to clarify contraindication to MRI also includes any inferences of significance to image quality	Clarification of rationale for exclusion criterion.
Section 5.5: Criteria for Initiation of Trial Treatment	To allow submission of screening knee x-rays for central read if acquired within 3 months of screening.	To reduce unnecessary radiographic imaging for the participants
Section 5.6.1: Process for Early Termination	Section added	To provide guidance on handling of early termination

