Survey for Autonomic Symptoms is a two-part questionnaire comprising 11 (for females) or 12 (for males) items, validated for assessing autonomic symptoms. For each item the participant will be asked if he/she have had the symptom the last 6 months (Yes/No) and, if Yes, how much would they say the symptom bothered them on a score ranging from 1 ("Not at all") to 5 ("A lot"). The overall score will be calculated as the sum of the responses, where "No" is scored as "0" and "Yes" responses are analyzed according to the score associated with how much the symptom bothered them. The number of participants with exactly one, exactly two, or three or more symptoms will be summarized. For the sum, individual missing responses will be imputed as the average of the non-missing responses. The average score will not be calculated if more than one response is missing. For the summary of the number of symptoms, missing responses will not be imputed. Participants with more than one missing response will be excluded from the number of symptoms summary unless the participant has checked "Yes" for three or more of the non-missing system responses.

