5. DATA HANDLING

5.1 Baseline and Study Visits

The last non-missing value, including unscheduled, prior to the first dose of study drug will be used as the Baseline value. Summaries presented by nominal collection day and/or by time point will be based on the schedule of assessments as planned in the protocol and as recorded on the eCRFs.

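### In the autonomic symptom-count table, a participant who enters with exactly 3 symptoms is already in the top category (3 or more), so no later rise in that participant's count can show

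*SAP*

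**What the plan says.** **Entry limit.** Protocol 5.2.3, criterion 21, excludes "Total score on Number of Symptoms (Column Q1a) on the SAS >3". Protocol 7.9.3 restates it: "with exclusion of participants with a score of > 3 (4 or more". Counts of 0, 1, 2 and 3 are therefore eligible. The scale goes far beyond that: "total score for the Number of symptoms score ranges from 0-11 (males) and 0-12 (females").

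**Timing.** The Schedule of Events places the survey at Visit 1 (screening), Visit 7 (Week 8) and Visit 11 (Week 20). SAP 5.1 sets baseline: "The last non-missing value, including unscheduled, prior to the first dose of study drug will be used as the Baseline value". Unless there is an unscheduled pre-dose survey, baseline is the screening count used for eligibility.

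**Planned count table.** SAP 4.9 says "The number of participants with exactly one, exactly two, or three or more symptoms will be summarized". SAP 4.14 instead describes cumulative categories: "Frequency and percentage of participants reporting at least 1, 2, or 3 symptoms according to the Survey for Autonomic Symptoms". Both stop at 3 or more. Neither section plans a change from baseline in the count, a shift table, or a row for 4 or more.

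**Other survey output.** SAP 4.14 adds: "The change from baseline in total symptom impact score according to the Survey for Autonomic Symptoms will be summarized", by gender, treatment and visit. It plans no formal testing of the survey, and SAP 4.1 has all collected data listed.

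**The concern.** The top category of a safety count should leave room for a participant to get worse. Here it begins at the highest count a participant may have at entry. For someone who enters with 3, the table reads the same at Week 20 whether the count is 3, 4 or 11. The report also could not state, by arm, how many participants rose above the level at which they could have been enrolled.

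Protocol 3.2 cites adverse effects on the sympathetic nervous system as a safety concern with anti-NGF antibodies, and this survey is the trial's item-by-item count of autonomic symptoms. What is at stake is how clearly a descriptive safety table can show worsening.

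**Working it through.** The plan gives no figure for this point, so there is none to reproduce. The first step needs no assumption. The others do.

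**1. Which rises are hidden.** Let c be the count; the planned category is min(c, 3). Take each eligible baseline and every higher count up to 11 (males) or 12 (females), the ranges in Protocol 7.9.3.

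| Baseline count | Possible rises (M / F) | Rises with category unchanged (M / F) | Same, with a 4-or-more category, min(c, 4) |
|---|---|---|---|
| 0 | 11 / 12 | 0 / 0 | 0 / 0 |
| 1 | 10 / 11 | 0 / 0 | 0 / 0 |
| 2 | 9 / 10 | 0 / 0 | 0 / 0 |
| 3 | 8 / 9 | 8 / 9 | 0 / 0 |

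The loss is complete for a baseline of exactly 3 and absent for all others. Nobody who meets criterion 21 can be in 4 or more at the screening survey.

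**2. How many enter at 3.** Not given. Assume a Poisson baseline with mean m, truncated to 0-3. The share at 3 is (m³/6) / (1 + m + m²/2 + m³/6).

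- m = 0.75: 0.0703 / 2.1016 = 3.3%
- m = 1.0: 0.1667 / 2.6667 = 6.25%
- m = 1.5: 0.5625 / 4.1875 = 13.4%
- m = 0.3: 0.0045 / 1.3495 = 0.3%

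The last value is prompted by Protocol 3.3.2.1.1, where 25.0% of healthy volunteers had autonomic symptoms at least once before or after dosing: -ln(0.75) = 0.29. That is a different population. With 416/4 = 104 per arm, the four shares are about 3, 6 or 7, 14, and fewer than 1 participant per arm.

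**3. An extreme case of masking.** Suppose 10% of each arm enter at 3, half of them rise in one active arm, none rise on placebo, and nobody else changes. Then 3 or more reads 10% in both arms, while 4 or more reads 5% against 0%.

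**4. A uniform effect.** Follow-up count = Binomial(baseline, 0.8) + Binomial(12 - baseline, r), with r = 0.02 on placebo and 0.06 on active. Contrast in standard errors = (p₁ - p₀) / √[p₁(1 - p₁)/104 + p₀(1 - p₀)/104].

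| Baseline mean | Category | Placebo | Active | Standard errors |
|---|---|---|---|---|
| 1.0 | 3 or more | 6.6% | 16.1% | 2.2 |
| 1.0 | 4 or more | 0.8% | 4.1% | 1.5 |
| 1.5 | 3 or more | 11.6% | 23.1% | 2.2 |
| 1.5 | 4 or more | 1.5% | 6.5% | 1.8 |

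Under a uniform effect the planned category separates the arms better. The two categories answer different questions, and both are worth reporting.

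**The case against.** Most of the opposing case stands, and it limits the point.

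- **Few participants may be affected.** Only those entering at exactly 3 are concerned, which is a minority under every assumption in step 2. The protocol's amendment log says the criterion 21 "cut-off increased to include a score of 3" in the light of emerging screening data. That suggests such counts were seen, but not how often.
- **Other outputs help.** Each added symptom adds 1 to 5 points to the impact score, which has no cap at 3 symptoms. Listings show individual counts, and symptoms reported as adverse events enter the TEAE tables. The cover is partial. Three symptoms can score 3-15 and four can score 4-20, so a new symptom may be offset by less bother. Listings do not compare arms, and adverse-event reports are not an item-by-item count.
- **Low stakes.** The survey is not a listed safety endpoint in either objectives table, and its summary carries no test.
- **The two SAP definitions hold nearly the same information.** Exclusive counts follow from cumulative ones by subtraction. They are still two specifications of one table.

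Three stronger readings are tempting, and the documents do not support them. A reader might infer that the table cannot show worsening at all, but every rise from 0, 1 or 2 changes category. A reader might take 4 or more as a level the protocol calls abnormal, but it is only an eligibility cut-off. A reader might conclude that 4 or more should replace 3 or more, but step 4 shows that 3 or more can be the more sensitive contrast.

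**Conclusion.** The point holds in a narrow form and is minor. In the symptom-count table of SAP 4.9 and 4.14, no rise from a baseline of exactly 3 can show: 8 of 8 possible rises for males and 9 of 9 for females. This follows from the stated rules alone, with baseline taken as the screening count.

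The number of participants concerned is unknown. It is about 3-13% under assumed truncated Poisson means of 0.75 to 1.5, and about 0.3% at a mean near 0.3. The masking in step 3 arises only if the harm falls on those who entered at 3. No type 1 error, power or decision rule is affected. The loss is in describing autonomic worsening among participants nearest the entry limit.

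**What to change.** 1. Replace the two SAP definitions with one set of exclusive categories: 0, 1, 2, 3, and 4 or more.
2. Keep 3 or more as a reported line, since it can be the more sensitive contrast.
3. Add a shift table by arm from baseline to Weeks 8 and 20, with the number newly at 4 or more. Label that level as the first count above the entry limit, not as an abnormal level.
4. Align the missing-item exception in SAP 4.9. It now keeps a participant with more than one missing response if at least three symptoms are present. That settles membership of 3 or more, but cannot tell 3 from 4 or more. The five-category table needs the exception at four; the 3-or-more line can keep the present one.
5. While editing, reconcile the item counts: SAP 4.9 gives 11 for females and 12 for males, and Protocol 7.9.3 gives the reverse.

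The cost is SAP wording and one extra table. The item responses are already collected, so no visit or assessment changes.
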